## 3 OBJECTIVES AND OUTCOME MEASURES/ENDPOINTS

### 3.1 Aims

The primary aim is to assess whether Cognitive Muscular Therapy (CMT) + usual care results in less knee pain and disability at 1-year post-randomisation compared to usual care alone. We hypothesise that CMT + usual care will be associated with lower composite WOMAC scores at 1 year in comparison to usual care alone for people with a clinical diagnosis of knee OA (OA), who are dissatisfied with the outcome of therapeutic exercise.

Secondary aims include:

- Estimates of treatment effects across a range of secondary outcomes including knee pain, knee function, knee stiffness, pain catastrophizing, pain self-efficacy, global assessment of knee symptoms, quality of life, the impact of knee OA on capacity to work, healthcare use (including knee replacement surgery) and adverse events up to 12-months.
- Within-trial cost utility analysis from an NHS and PSS perspective.
- Qualitative exploration of participants and physiotherapists' experiences and perception of the CMT intervention, beliefs around implementation and involvement in the trial.

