### 3.3 Secondary Outcome measures and endpoints

- Composite WOMAC score [19] at 6-months post-randomisation
- WOMAC pain subscale [19] at 6- and 12-months post-randomisation
- WOMAC function subscale [19] at 6- and 12-months post-randomisation
- WOMAC stiffness subscale [19] at 6- and 12-months post-randomisation
- Global assessment of knee symptoms (GAKS) at 6- and 12-months post-randomisation [24]

- Pain catastrophizing scale (PCS) [25] at 6- and 12-months post-randomisation
- Pain self-efficacy questionnaire (PSEQ) [26] at 6- and 12-months post-randomisation
- Impact of knee OA on capacity to work will be measured with the Work Productivity and Activity Impairment Questionnaire (WPAI-OA) [27] at 6- and 12-months post-randomisation.
- Health-related quality of life will be measured using the EQ-5D-5L at 6- and 12-months post-randomisation. The EQ-5D-5L [28] is a validated measure of health-related quality of life in terms of 5 dimensions (mobility, ability to self-care, ability to undertake usual activities, pain and discomfort, anxiety and depression) each with 5 levels of severity.
- Healthcare resource use at 6- and 12-months will be measured via a custom questionnaire, based on the Client Services Receipt Inventory. Included within this questionnaire will be additional physiotherapy (above that provided to the CMT arm), GP appointments, corticosteroid injections, surgery, imaging, hospital stays and medication use.
- All-cause mortality.
- Adverse events attributable to the trial.
- Serious adverse events.

Our choice of outcomes includes instruments to capture pain, stiffness, activity limitation, psychological factors, global assessment of knee symptoms, quality of life, healthcare resource utilisation and adverse events, including mortality. This outcome set is sufficiently broad to include all components of a core outcome set recommended by OMERACT-OARSI (Outcome Measures in Rheumatology-Osteoarthritis Research Society International) for clinical trials in knee osteoarthritis [24].

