##### AEs exempt from formal recording

For the intervention group, common AEs listed below that are identified during or after intervention sessions will be recorded on the treatment log (not an AE form), for clinical purposes only:

- Any accidents (e.g. falls) which occur during normal daily activities
- Exacerbation of pre-existing musculoskeletal conditions (including knee pain) which last no more than five days

Any AEs that are not listed above should be recorded using the AE form (See 'Adverse events form'). Forms should be completed by the treating physiotherapist as soon as possible after becoming aware of the AE and sent to the study team. All AEs should be assessed within 24 hours of identification to check if they constitute a 'Serious Adverse Event' as per section 9.1.2 below. If assessed as a Serious Adverse Event, it should be reported within 24 hours, following the procedures outlined in section 9.2.4.

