## 9.2 Recording Adverse Events and Reporting Serious Adverse Events

### 9.2.1 Recording and reporting period

Intervention (CMT) group: All AEs and SAEs (unless otherwise specified) occurring from the time of informed consent until the six-month follow-up time-point must be recorded and reported as appropriate. Participants will be asked about anything that might constitute a SAE at the six-month follow-up questionnaire (see 'Adverse event question') and will also be given the opportunity to identify any events at every face-to-face physiotherapy session or via email/letter (sent to the trial team) during the intervention period.

Usual care group: The usual care group will be asked about anything that might constitute a SAE during the six-month follow-up questionnaire only questionnaire (see 'Adverse event question'). It will not be possible to collect a comparison dataset for the usual care group within this period without contaminating usual care. This is a pragmatic study, and the participants will not be contacted during the intervention period, unlike the intervention group. It is important not to contact the usual care group more than is necessary so as not to introduce bias. We anticipate a low risk of adverse events arising from usual NHS care.

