### 9.2.2 Recording and assessing AEs/SAEs

Participants in the intervention group will be asked about any potential AEs at the start of each face-to-face physiotherapy session. In addition, during the session the treating physiotherapist will monitor for any indications of an AE. Potentially AEs will be evaluated by the treating physiotherapist with follow-up contact from the research team to confirm the details. Participants in the intervention group will also be provided with contact details (generic email address and phone number) for the study team. Whilst participants will not be actively encouraged to report AEs via this route, they may seek advice and help from the study team which may result in AEs being disclosed/discussed. Any AEs, with the exception of those listed in Section 9.1.1, will be recorded on the AE form and stored on the secure trial database unless they fulfil the criteria for a 'Serious Adverse Event' in which case they will be reported to the sponsor via the SAE form (see Section 9.2.3 below).

All AEs should be assessed by an appropriately qualified member of the study team within 72 hours of identification to determine if they meet the criteria to be reported as SAEs as defined in Section 9.1.2. If any AEs meet these criteria, they must be reported to the sponsor within a further 24 hours. If the follow-up questionnaire received from a participant indicates events that may fulfil an SAE, then they should be contacted for further information and an SAE form completed if applicable.

All SAEs should be reported to study team (using the document 'Serious Adverse Event Form'), irrespective of their relationship to the intervention unless they are exempt from reporting (see Section 9.1.2). Once received, the study team review the SAE and request further information if required from the treating physiotherapist or participant appropriate.

The causality of SAEs (i.e. relationship to study intervention) will be assessed by the chief investigator and another appropriately delegated member of the trial team using the classifications in Table 5 below.

Table 3: SAE Causal relationships

Relationship to study intervention	Description
Unrelated	There is no evidence of any causal relationship.

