## 9.4 Notification of deaths

All deaths, when they are identified (up to the 12-month follow-up time-point), will be reported to the sponsor by the study team overseen by the CI, irrespective of whether the death is intervention-related, or an unrelated event. Deaths identified between six and 12 post-randomisation will be recorded for outcomes purposes but will not be classed as an SAE.

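### Section 3.1 promises adverse-event treatment effects to 12 months, but AE/SAE enquiry stops at 6 months and differs by arm, so the aim cannot be met as written

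*Protocol*

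**What the plan says.** The secondary aims in section 3.1 begin with "Estimates of treatment effects across a range of secondary outcomes including knee pain, knee function, knee stiffness" and run on to "healthcare use (including knee replacement surgery) and adverse events up to 12-months". Section 3.3 lists "Adverse events attributable to the trial", serious adverse events and all-cause mortality as secondary outcomes, without time points.

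Section 9.2.1 sets the recording period. In the CMT arm, AEs and SAEs are recorded from consent to the six-month time-point. Participants are asked about possible SAEs in the six-month questionnaire, "will also be given the opportunity to identify any events at every face-to-face physiotherapy session", and may also write to the trial team. Section 9.2.2 adds that they are asked about AEs at the start of each session. For the other arm: "The usual care group will be asked about anything that might constitute a SAE during the six-month follow-up questionnaire only". The protocol explains that a comparison dataset cannot be gathered in usual care during this period without contaminating it, and that extra contact could introduce bias.

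Table 2 marks adverse events for the intervention period and 6 months, not for 12 months; deaths are marked through to 12 months. Section 8.7 has both arms complete questionnaires at 6 and 12 months.

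On timing, section 9.1.1 says "All AEs should be assessed within 24 hours of identification" to check for seriousness. Section 9.2.2 has the study team do this "within 72 hours of identification to determine if they meet the criteria to be reported as SAEs".

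**The concern.** An aim to estimate a treatment effect on adverse events to 12 months needs two things: events sought over 12 months, and events sought in the same way in both arms. The protocol provides neither. The gap lies in data collection, so it cannot be left to an analysis plan.

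SAEs and attributable AEs are listed secondary outcomes. A reader of the final report could take a table of events by arm as a fair comparison over the year. As planned, it would cover half the year, have no usual-care data for non-serious events, and might mix events found by repeated face-to-face enquiry with events found by a single questionnaire item.

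**Working it through.** No stated figure needs reproducing here. The check sets the promise against the collection plan and counts the scheduled enquiries.

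**Horizon.** Promised in 3.1: 12 months. Collected under 9.2.1 and Table 2: 6 months. Uncovered: 12 − 6 = 6 months, or 6/12 = 50% of the promised period, in both arms.

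**Enquiries by arm** (seven sessions from 6.2; prompts from 9.2.1 and 9.2.2; other sources from 3.3, 9.4 and Table 2):

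| | CMT | Usual care |
|---|---|---|
| Session enquiries about any AE, to month 6 | up to 7 | 0 |
| Six-month questionnaire item on possible SAEs | 1 | 1 |
| AE/SAE enquiry, months 6–12 | 0 | 0 |
| Deaths to 12 months | yes | yes |
| Surgery and hospital stays at 6 and 12 months (resource-use questionnaire) | yes | yes |

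For non-serious AEs, usual care has no scheduled enquiry, so a between-arm estimate is impossible rather than merely biased.

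For SAEs, the CMT arm has at most 7 + 1 = 8 enquiries against 1. Eight applies only to someone who attends every session, and it mixes two kinds of prompt: the session prompt covers any AE, the questionnaire item possible SAEs. The questionnaire prompt alone is 1 against 1.

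The telephone minimum dataset in 8.8 consists of WOMAC, GAKS and EQ-5D-5L. It shows no adverse event item, so a usual-care participant reached only by that call has no planned enquiry, whereas a CMT participant may already have reported at a session.

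**Direction of bias in an SAE comparison.** Observed ratio = true ratio × (share of events captured in CMT ÷ share captured in usual care). If both arms count only answers to the questionnaire item, the instrument is the same. If session reports are added for CMT, its captured share can only stay the same or rise, which pushes the observed ratio up and makes CMT look less safe. The documents give no capture shares, so only the direction can be stated.

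**After the change proposed below.** The same question at 6 and 12 months gives 2 prompts against 2, and 12 of 12 months are covered.

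**Assessment times.** Sections 9.1.1 and 9.2.2 each refer to all AEs and each count from identification, but one allows 24 hours and the other 72, a difference of 48 hours. The two passages must be reconciled.

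**The case against.** The strongest reply is that the protocol never commits to a modelled comparison of adverse events. The 12-month horizon for them appears in one clause of a list of aims. Section 3.3 gives no time point, and attributable events are largely a description of the CMT arm. Section 10.5 leaves AEs, SAEs and mortality out of the outcomes to be analysed by model. Section 9.2.1 discloses the asymmetry and gives a reason. Both arms already get the same SAE question at 6 months, so a like-for-like 6-month comparison is available, and the choice of events for a safety table may properly sit in an analysis plan that is not shown.

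Most of this stands, and it limits the point. The bias is conditional: no passage says that session and questionnaire events will be pooled, and none says that they will be kept apart. It does not remove the conflict, because section 3.1 still promises treatment effects to 12 months. The reason in 9.2.1 concerns extra contact during the intervention period. It does not explain the absence of the question from a 12-month questionnaire that both arms already receive.

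On the assessment times, two steps may be intended: 9.1.1 follows instructions to the treating physiotherapist, while 9.2.2 names the study team. The text does not say so.

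**Conclusion.** The point holds as an internal contradiction. The collection plan cannot deliver the section 3.1 aim: 6 of 12 months have no AE/SAE enquiry, non-serious AEs have no usual-care data, and scheduled SAE enquiries run at up to 8 against 1. A between-arm SAE comparison would be biased, probably against CMT, if session-detected events were pooled with questionnaire events. That last statement assumes pooling, and also that repeated enquiry finds more events than a single item.

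Three stronger readings are tempting but unsupported:

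- A reader might infer that months 6 to 12 are unobserved for safety. They are not: deaths, hospital stays and surgery are captured in both arms. These are not AE/SAE records, but they do cover the period.
- A reader might want to attach a size to the bias. The documents give no capture rates, so any ratio would reflect only the rates assumed.
- A reader might see an error in the rule that deaths after month 6 "will be recorded for outcomes purposes but will not be classed as an SAE". That rule follows from the six-month SAE window. The deaths are still reported to the sponsor and counted as an outcome, so nothing is lost.

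The discrepancy in assessment times is a separate textual matter and adds nothing to the weight of the main point.

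**What to change.** Preferred change:

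- Add the existing adverse event question to the 12-month questionnaire in both arms, mark it at 12 months in Table 2, and extend the period in 9.2.1 to match. Wording elsewhere that relies on the six-month window, as in 9.4, would follow.
- State that the between-arm SAE comparison uses only answers to that question at 6 and 12 months, by randomised arm. An event given in answer counts whether or not it was also reported at a session.
- Describe events found at sessions, or by email or letter, separately as CMT-arm data, with no between-arm estimate for non-serious AEs.
- Say whether the telephone minimum dataset includes the question.

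The cost is one existing item on an existing questionnaire, some extra SAE clarification, causality assessment and reporting after month 6, and an amendment. No new scheduled contact with usual care is needed. The change is best made before 12-month questionnaires go out.

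Alternative: restate the 3.1 aim as a 6-month, questionnaire-based SAE comparison with no between-arm estimate for non-serious AEs, and give the matching time points in 3.3. This changes wording only, but leaves months 6 to 12 without an AE/SAE enquiry.

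In either case, reconcile the assessment times in 9.1.1 and 9.2.2. If two steps are meant, say who does each and when.

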### 9.2.2 Recording and assessing AEs/SAEs

Participants in the intervention group will be asked about any potential AEs at the start of each face-to-face physiotherapy session. In addition, during the session the treating physiotherapist will monitor for any indications of an AE. Potentially AEs will be evaluated by the treating physiotherapist with follow-up contact from the research team to confirm the details. Participants in the intervention group will also be provided with contact details (generic email address and phone number) for the study team. Whilst participants will not be actively encouraged to report AEs via this route, they may seek advice and help from the study team which may result in AEs being disclosed/discussed. Any AEs, with the exception of those listed in Section 9.1.1, will be recorded on the AE form and stored on the secure trial database unless they fulfil the criteria for a 'Serious Adverse Event' in which case they will be reported to the sponsor via the SAE form (see Section 9.2.3 below).

All AEs should be assessed by an appropriately qualified member of the study team within 72 hours of identification to determine if they meet the criteria to be reported as SAEs as defined in Section 9.1.2. If any AEs meet these criteria, they must be reported to the sponsor within a further 24 hours. If the follow-up questionnaire received from a participant indicates events that may fulfil an SAE, then they should be contacted for further information and an SAE form completed if applicable.

All SAEs should be reported to study team (using the document 'Serious Adverse Event Form'), irrespective of their relationship to the intervention unless they are exempt from reporting (see Section 9.1.2). Once received, the study team review the SAE and request further information if required from the treating physiotherapist or participant appropriate.

The causality of SAEs (i.e. relationship to study intervention) will be assessed by the chief investigator and another appropriately delegated member of the trial team using the classifications in Table 5 below.

Table 3: SAE Causal relationships

Relationship to study intervention	Description
Unrelated	There is no evidence of any causal relationship.
Unlikely to be related	There is little evidence to suggest there is a causal relationship (e.g. the event did not occur within a reasonable time after administration of the study intervention). There is another reasonable explanation for the event (e.g. the patient's clinical condition, other concomitant treatment).
Possible relationship	There is some evidence to suggest a causal relationship (e.g. because the event occurs within a reasonable time after administration of the study intervention). However, the influence of other factors may have contributed to the event (e.g. the patient's clinical condition, other concomitant treatments).
Probable relationship	There is evidence to suggest a causal relationship and the influence of other factors is unlikely.
Definitely related	There is clear evidence to suggest a causal relationship and other possible contributing factors can be ruled out.

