### 10.3 Summary of baseline data and flow of participants

Analyses will be reported in line with the CONSORT statement. Descriptive statistics will be presented to summarise the distribution of baseline variables across each of the two randomisation groups. The continuous baseline variables (age, height, weight, duration of knee pain symptoms) will be reported with means & standard deviations, if shown to be normally distributed, using a combined skewness and kurtosis test, otherwise will be reported with medians and interquartile ranges (IQR).

A Consolidated Standards of Reporting Trials (CONSORT) flow diagram will be produced, showing the frequency of participants:

- Screened for eligibility
- Reason for not being eligible,
- Found eligible,
- Reasons not approached,
- Approached
- Excluded before consent and reason for exclusion
- Consented
- Excluded before randomisation and reason for exclusion,
- Randomised
- Allocated to each randomisation group
- That received each allocated intervention
- That did not receive each allocated intervention
- Lost to follow-up (and the frequency of each reason for loss to follow-up) for each analysis group,
- Analysed for each analysis group,
- Not analysed (and the frequency of each reason for not being analysed) for each analysis group.

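### Non-serious adverse events in the CMT arm are asked about only at attended sessions, although section 9.2.1 requires all of them to be recorded to six months

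*Protocol*

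**What the plan says.** For the CMT group, section 9.2.1 states: "All AEs and SAEs (unless otherwise specified) occurring from the time of informed consent until the six-month follow-up time-point must be recorded". The exemptions in section 9.1.1 are limited to accidents in ordinary daily life and flares of existing musculoskeletal conditions lasting five days or less. AEs attributable to the trial are a secondary outcome in section 3.3, listed separately from serious adverse events (SAEs).

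The means of collection are these:

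- **At sessions.** Section 9.2.2: "Participants in the intervention group will be asked about any potential AEs at the start of each face-to-face physiotherapy session". It adds that "during the session the treating physiotherapist will monitor for any indications of an AE". Table 4 in section 9.3 likewise ties the physiotherapist's check to attendance.
- **At six months.** Section 9.2.1: "Participants will be asked about anything that might constitute a SAE at the six-month follow-up questionnaire". Table 2 in section 8.7, however, marks a row for adverse events in general at that visit.
- **By contact with the team.** Section 9.2.1 lets participants raise events "via email/letter (sent to the trial team) during the intervention period". Section 9.2.2 gives them an e-mail address and phone number but qualifies this: "Whilst participants will not be actively encouraged to report AEs via this route".
- **On stopping CMT.** Sections 6.8 and 8.10 offer a choice between continuing with outcomes and full withdrawal, and require the change to be documented. Neither asks for an AE enquiry or a reason.

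**The concern.** The duty covers a period; the active enquiry covers attendance. Two groups of non-serious events fall between them.

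First, an event that develops after one session is asked about at the next. A participant who does not return because of it is not asked. Being asked then depends on coming back, and coming back may depend on not having been harmed.

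Second, once the last session is over nobody asks about non-serious events, although section 6.2 encourages participants to go on practising at home.

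At stake is how the harms result for CMT can be read. Section 6.2 already describes the intervention as carrying very little risk. A low recorded count would seem to confirm this while partly reflecting who was asked. The participants least observed would be those attending fewer than six sessions, whom the primary estimand in section 10.4 keeps in the comparison.

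**Working it through.** **Step 1: does an exemption remove the duty?** Section 9.2.1 allows for exceptions specified elsewhere. Those in section 9.1.1 are defined by type and duration of event. None excludes events after the last session or after stopping. A knee-pain flare of more than five days, for example, remains recordable throughout.

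**Step 2: which source solicits which non-serious event?**

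| When the event arises | Active enquiry |
|---|---|
| Between consent and session 1 | Yes, at session 1 if attended |
| During a session | Yes, physiotherapist monitoring |
| Between two attended sessions | Yes, at the next session |
| After a session, participant does not return | None stated |
| After the last session, up to six months | None stated (six-month question described as SAE-only) |

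**Step 3: length of the gap.** Inputs from section 8.7: treatment to start within 7 weeks of randomisation; delivery over 7-9 weeks; completion by four months; upper limit six months. One month is 52.18 / 12 = 4.35 weeks, so six months is 26.1 weeks and four months is 17.4 weeks.

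The plan's own figure reproduces: 7 + 7 = 14 weeks (3.2 months) and 7 + 9 = 16 weeks (3.7 months), both within four months.

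Gap = 26.1 weeks minus the week of the last session:

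- Sessions end at four months: 26.1 - 17.4 = 8.7 weeks, or 2 of 6 months (33%).
- Start at week 7, delivery over 9 weeks: 26.1 - 16 = 10.1 weeks (39%).
- Start at week 7, delivery over 7 weeks: 26.1 - 14 = 12.1 weeks (46%).
- Sessions run to the six-month limit: 0 weeks.

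For someone who stops early, the gap runs from the last attended session. Assuming a start at week 7, weekly sessions and attendance at three, the last falls at about week 10 on the same counting, and the gap is 26.1 - 10 = 16.1 weeks (62%).

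These percentages are shares of the post-randomisation period. The recording window opens at consent, and section 8.7 allows baseline collection to be delayed by up to two months. With that full delay, the two-month gap is about 2 / 8 = 25% of the whole window.

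**Step 4: number of events missed.** This cannot be calculated. It needs the rate of related non-serious events, the share leading to non-return and the share volunteered anyway. The protocol gives none of these. Its only figure, no adverse events in over 200 people treated (section 6.2), comes without a description of how events were sought.

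**The case against.** The strongest reply is that events are watched for where they are most likely. Section 6.2 names the foreseen harms, skin reaction to the sensors and dizziness from the breathing exercises, and has the physiotherapist monitor for both. That stands: events during any session, including the last, are covered.

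Nor are later events impossible to capture. Participants hold contact details, and one who asks to discontinue is by then in touch with the team. Withdrawals are documented (section 8.10), and the steering committee sees treatment withdrawals, adherence and adverse events. That also stands, but none of these steps requires anyone to ask about an AE.

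The wording of the 'Adverse event question' is not shown, and Table 2 could mean that it covers all AEs. If so, the gap after the last session would narrow for those who return the questionnaire, and section 9.2.1 would be the passage to correct. As written, section 9.2.1 describes the question as limited to possible SAEs.

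A reader might infer more than the protocol supports:

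- That non-serious events after the last session or after stopping cannot be recorded at all. They are unsolicited, not uncapturable.
- That nearly three quarters of the six months is unobserved for completers. This needs treatment to begin at randomisation (26.1 - 7 = 19.1 weeks, 73%), whereas section 8.7 has scheduling begin only after randomisation.
- That a given fraction of CMT harms will be lost. No such fraction can be derived.
- That the flow-diagram item "That did not receive each allocated intervention" is defective because it does not ask for reasons. That is reporting detail which can be settled elsewhere.

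**Conclusion.** The point holds as a mismatch between a stated duty and the stated means. Section 9.2.1 requires that non-exempt events "occurring from the time of informed consent until the six-month follow-up time-point must be recorded and reported as appropriate", while sections 9.2.1 and 9.2.2 provide active enquiry about non-serious events only at attended sessions. For completers the gap is about two of the six post-randomisation months if sessions end at four months, about 10 to 12 weeks with a start at week 7, and nil at the six-month limit. For those who stop early it is longer.

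The likely direction is under-counting of attributable AEs in the CMT arm, most of all among people who stop because of an event. The size is unknown. The conclusion assumes that the six-month question is as section 9.2.1 describes it and that events nobody asks about are reported less often than events somebody asks about. SAEs are solicited at six months and are not affected.

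**What to change.** Reconcile sections 9.2.1 and 9.2.2 and Table 2 as follows:

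- **(a)** Word the existing six-month 'Adverse event question' to cover any new or worsened health problem in the period, identically in both arms.
- **(b)** When a CMT participant stops attending or asks to discontinue, have the intervention coordinator, who already liaises with that arm on scheduling (section 8.7), ask the AE question and record the reason for stopping if one is given.

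If this is not wanted, restate the window for non-serious AEs as ending at the last attended session, and report AEs on that basis.

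The cost is one reworded questionnaire item, a sentence in section 9.2.2 and a short enquiry for each participant who stops. Item (a) adds no contact with usual care, so it respects the reason section 9.2.1 gives for limiting that contact. The downside is more minor events to review. Item (b) applies to the CMT arm only, so events found that way should be reported as CMT-arm harms and not used in a between-arm comparison.
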